9.10.4.3 Other Laboratory Assessments

Subjects will be asked to provide serum and urine at the times indicated in the Schedule of Events ([Table 9.1.1](#)).

For subjects who have not had genetic testing confirming diagnosis of ACH, molecular genetic diagnosis to identify the FGFR3 mutation (G346E, G375C, G380R, or “other”) will be performed. If subjects had previous genetic testing, subjects must have either a written letter by the physician confirming genetic testing, including the specific mutation, or a lab certification with the study specific mutation documented.

9.10.4.4 Vital Signs, Physical Examinations and Other Observations Related to Safety

9.10.4.4.1 Vital Signs

Vital signs will include seated systolic blood pressure (SBP) and diastolic blood pressure (DBP) measured in mm Hg, heart rate in beats per minute, respiration rate in breaths per minute, and temperature in degrees Celsius (°C). All treatment visits have pre-dose vital sign assessments. Post-dose assessments include heart rate and BP. On visit Days 1, 2, 3, and 4, minimum assessment frequency is every 15 min (± 5 min) for 2 hours post dose; and assessment is taken every 30 min (± 5 min) from 2 to 4 hours post dose. On visit Days 1 and 2, 4 to 8 hours post-dose measurements are taken every 60 min (± 10 min). For all other dosing visits, assessment is every 15 min (± 5 min) for the first hour post dose and a final assessment prior to the end of the visit (if longer than 1 hour). Vital sign assessment frequency is presented in [Table 9.10.4.4.1.1](#).

At Screening, after at least 5 minutes of rest, subject’s BP is taken in sitting position. Then the subject will stand and BP will be taken again at approximately 1 and 3 minutes after standing. At other visits, vital sign measurements are taken once per timepoint in a sitting position after at least 5 minutes of rest. Heart rate should be taken at each timepoint that BP is measured. When blood samples and BP assessments are scheduled at the same time or within the same time window, BP should be measured before blood samples are drawn. If a BP measurement must be taken after a blood draw, ensure adequate analgesia for the blood draw and wait several minutes before measuring BP. Vital signs may be monitored more frequently or for longer duration post-dose as clinically indicated ([Table 9.1.1](#)).

	BMN 111-202 Amendment 4	Page 71
---	-------------------------	---------

Table 9.10.4.4.1.1: Vital Sign Assessment Frequency

Vital Sign Assessment Frequency				
Screening	After at least 5 min of rest, subject's BP is taken in sitting position. Then the subject will stand and BP will be taken again at approximately 1 and 3 minutes after standing.			
	Assessment Frequency			
Dosing Visits	0-1 hr post-dose	0-2 hr post-dose	2-4 hr post dose	4-8 hr post-dose
Days 1, 2		q 15 min (± 5 min)	q 30 min (± 5 min)	q 60 min (± 10 min)
Days 3, 4 and dose adjustment visit in optional, open-label extension phase		q 15 min (± 5 min)	q 30 min (± 5 min)	
All other dosing visits	q 15 min (± 5 min); final assessment prior to end of visit (if longer than 1 hr). Includes dose adjustment and follow up visits.			

 Vital sign measurements are taken once per timepoint in a sitting position after at least 5 minutes of rest. Left brachial arm should be the first method of assessment considered, and the same site should be used for measurement of BP in each subject throughout the study. Heart rate should be taken at each timepoint that BP is measured. When blood samples and BP assessments are scheduled at the same time or within the same time window, BP should be measured before blood samples are drawn. If a BP measurement must be taken after a blood draw, ensure adequate analgesia for the blood draw and wait several minutes before measuring BP. Vital signs may be monitored more frequently or for longer duration post-dose as clinically indicated. If a subject has a hypotensive event (or symptoms potentially consistent with hypotension) or a decrease in systolic BP of 20 mm Hg or more from pre-dose systolic BP, blood pressure and heart rate (BP/HR) should be measured and recorded approximately every 15 minutes for the first hour and every 30 minutes thereafter until the systolic BP returns to pre-dose systolic BP (or within the normal range for this subject as defined by PI) and symptoms (if present) resolve. 				

9.10.4.4.2 Mitigating the Risk of Potential Hypotension

Study personnel and caregivers should be aware of the potential risk of hypotension with BMN 111 administration. Subjects must be well hydrated and have eaten breakfast prior to administration of BMN 111. In the hour prior to injection, all subjects should have attempted to drink 8 ounces (~250 ml) of fluid (e.g. water, milk, juice, etc.), and the outcome must be documented by the site on clinic visit days. Caregivers should be trained to observe and recognize the symptoms of dehydration (e.g. from fever, vomiting, diarrhea, etc.) and contact the Investigator prior to study drug administration if dehydration is suspected. Site personnel

and caregivers should be trained to identify the symptoms of hypotension and, if they occur, should implement first-aid strategies at the discretion of the investigator such as having the subject lie down supine, elevating the lower extremities, and administering fluids. For guidelines on how to report adverse events associated with hypotension, refer to Section 10.

9.10.4.4.3 Hip Monitoring

Baseline hip assessments will be conducted for all cohorts, and will include medical history, physical exam, and AP x-ray of the pelvis. Subsequent hip monitoring assessments will be conducted at regular 6-month intervals. Medical history will be obtained to evaluate for hip, thigh, or knee pain, or change in gait. The physical exam will include supine and prone assessment to determine pain or limitation with hip range of motion and internal/external rotation of hip joint. Changes from baseline will trigger further evaluation, which may include additional hip imaging, and/or orthopedic consultation. DMC will be notified of abnormal results from hip monitoring assessments to determine if/when BMN 111 treatment should be temporarily or permanently discontinued, or dose reduced.

9.10.4.4.4 ECGs

A standard 12-lead ECG will include heart rate, rhythm, intervals, axis, conduction defects, and anatomic abnormalities. If clinically significant abnormalities are noted, the Investigator or designee is required to assess whether it is appropriate for the subject to continue in the study. ECGs will be performed at the time points indicated in the Schedule of Events (Table 9.1.1).

9.10.4.4.5 ECHO

Cardiac anatomy and function will be evaluated by a standard 2-dimensional Doppler ECHO. The data recorded is to include ventricular cavity size, valve characterization (presence or absence of valve stenosis or regurgitation and clinical significance), ventricular wall thickness, regional wall motion, LV mass calculation, and pericardial characterization. ECHOs will be performed at the time points indicated in the Schedule of Events (Table 9.1.1).

9.10.4.4.6 Anti-BMN 111 Immunogenicity Assessments and IgE Testing

9.10.4.4.6.1 Scheduled Immunogenicity Assessments

Blood serum sampling for immunogenicity assessments will be performed at the time points indicated in the Schedule of Events (Table 9.1.1 and Table 9.1.2).

Scheduled samples will be tested in one or more of the following assessments:

	BMN 111-202 Amendment 4	Page 73
---	-------------------------	---------

- Anti-BMN 111 total antibody (TAb)
- Endogenous CNP, ANP, and BNP cross-reactivity
- Anti-BMN 111 neutralizing antibody (NAb)

Testing for the presence of cross-reactive antibodies that bind to endogenous CNP, ANP, or BNP and for the presence of BMN 111-NAbs will be performed on baseline samples and anti-BMN111 TAb-positive samples.

9.10.4.4.6.2 Ad Hoc Safety Assessments

Samples for total IgE and drug-specific IgE testing will be drawn pre-dose on Day 1. If a significant hypersensitivity adverse event (defined as grade 3 or higher, or requiring temporary or permanent cessation of BMN 111, or at the discretion of Investigator and/or BioMarin, excluding reactions that are solely a localized injection site reaction) occurs, an unscheduled safety visit should occur within 48 hours of the start of the reaction, including inspection of the injection site and clinical laboratory tests. Blood serum samples should be collected and tested in one or more of the following assessments:

- Anti-BMN 111 IgE (drug-specific IgE)
- Total IgE
- Serum tryptase

If feasible, a sample for drug-specific IgE should be drawn at least 8 hours after the event start time and before the next dose. A sample for total IgE and serum tryptase should also be drawn within an hour of the start of the event when possible or during the unscheduled safety visit.

A localized injection site reaction is defined as skin signs or symptoms restricted to one affected primary location, i.e., hives, wheals, or swelling or an area of erythema, redness, induration, pain, or itching at or near the site of injection. Management of such localized reactions should be determined by the Investigator's clinical judgment in consultation with the Sponsor's Medical Monitor (if warranted).

9.10.4.5 Pregnancy Testing

Female subjects who have begun menses or are ≥ 10 years old will have a urine or serum pregnancy test at the time points specified in the Schedule of Events ([Table 9.1.1](#)). Female subjects with a positive pregnancy test at Screening do not meet eligibility criteria for enrollment ([Section 9.3.2](#)).

	BMN 111-202 Amendment 4	Page 74
---	-------------------------	---------

Serum pregnancy tests will be performed in the event that urine pregnancy test results are positive or equivocal.

Refer to Section [10.3.1.9](#) for details on the reporting procedures to follow in the event of pregnancy.

9.11 Pediatric Blood Volume

Clinical labs and immunogenicity samples are relevant to safety assessment in this study. The objective of the PK assessments is to understand the relationship between exposure and biologic activity. The objectives of exploring pharmacodynamic activity biomarkers are to demonstrate biologic activity of BMN 111 and to understand both the impact of immune responses on drug activity and the mechanisms of CV changes during dosing; and for bone and collagen biomarkers, to demonstrate activity at the growth plate (chondrocyte) and bone (osteoblast) levels.

To minimize blood collection volumes, assay technologies were chosen that are capable of sensitively detecting analytes using the lowest possible volume of blood for analysis. Additionally, assays capable of detecting analytes in urine rather than blood have been selected where possible.

10 REPORTING ADVERSE EVENTS

10.1 Safety Parameters and Definitions

Safety assessments will consist of monitoring and recording protocol-defined AEs and SAEs; measurement of protocol-specified hematology, clinical chemistry, and urinalysis variables; measurement of protocol-specified vital signs; and other protocol-defined events of special interest that are deemed critical to the safety evaluation of the study drug.

10.1.1 Adverse Events

For this protocol, a reportable AE is any untoward medical occurrence (eg, sign, symptom, illness, disease or injury) in a subject administered the study-drug or other protocol-imposed intervention, regardless of attribution. This includes the following:

- AEs not previously observed in the subject that emerge during the course of the study.
- Pre-existing medical conditions judged by the Investigator to have worsened in severity or frequency or changed in character during the study.
- Complications that occur as a result of non-drug protocol-imposed interventions (e.g., AEs related to screening procedures, medication washout, or no-treatment run-in).

An adverse drug reaction is any AE for which there is a reasonable possibility that the study drug caused the AE. “Reasonable possibility” means there is evidence to suggest a causal relationship between the study-drug and the AE.

Whenever possible, it is preferable to record a diagnosis as the AE term rather than a series of terms relating to a diagnosis.

10.1.2 Serious Adverse Events

A serious adverse event (SAE) is any untoward medical occurrence that at any dose meets one or more of the following criteria:

- Is fatal
- Is life threatening

Note: Life-threatening refers to an event that places the patient at immediate risk of death. This definition does not include a reaction that, had it occurred in a more severe form, might have caused death.

- Requires or prolongs inpatient hospitalization. Hospitalization for less than 24 hours will not be considered to be an SAE.

- Results in persistent or significant disability or incapacity
- Is a congenital anomaly or birth defect in the child or fetus of a patient exposed to IP prior to conception or during pregnancy
- Is an important medical event or reaction that, based on medical judgment, may jeopardize the patient or require intervention to prevent one of the above consequences (e.g., anaphylaxis)

All adverse events that do not meet any of the criteria for SAEs should be regarded as non-serious AEs.

10.2 Methods and Timing for Capturing and Assessing Safety Parameters

10.2.1 Adverse Event Reporting Period

The study AE reporting period is as follows: after informed consent but prior to initiation of study treatment, only SAEs associated with any protocol-imposed interventions will be reported. After informed consent is obtained and the first administration of study drug, all non-serious AEs and SAEs reporting period begins and continues until 4 weeks following either the last administration of study drug or the early termination visit, whichever is longer. The Month 25 Safety Follow-up Visit will be waived if a subject enrolls in the 111-205 extension study at the Month 24/Study Completion Visit. The criteria for determining, and the reporting of SAEs are provided in Section [10.1.2](#).

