7.1 Nonclinical Studies

The nonclinical studies characterized the primary pharmacodynamic activity of BMN 111 in normal mice, rats and cynomolgus monkeys and in two mouse models of ACH (TD [severe] and Ach [mild]). Respiratory and CNS safety pharmacology were evaluated in rats and CV safety pharmacology in telemeterized monkeys. Repeat-dose toxicity and TK GLP studies were completed including two 28-day studies: one in the young adult rat and one in the juvenile monkey, three 26-week studies: one in the juvenile rat, one in the adult rat and one in the juvenile monkey, and one 44-week study in sexually mature cynomolgus monkeys (with open growth plates).

Overall, BMN 111-related findings were limited to the known mechanism of action of CNP on the growth plate and vasculature, resulting in the promotion of longitudinal bone growth at hemodynamically tolerated dose levels. Additionally, reversible subcutaneous injection site reactions were reported, including injection site discoloration and microscopic findings

[figure not shown]
of perivascular mononuclear cell infiltrates that were seen with slightly higher incidence and severity in BMN111-treated rats and monkeys compared to the vehicle control. There were no BMN 111-related effects on respiratory, CNS, or sexual development and reproductive performance. Adverse skeletal changes associated with exaggerated growth were seen in all normal nonclinical species with open growth plates, and were dose-, exposure- and time-dependent. These effects included abnormally shaped femoral head, acetabular growth center/plate dysplasia and concomitant articular cartilage degeneration with clinical manifestations of restricted use of hips.

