- ^{aa} After written informed consent but before study treatment initiation, only SAEs associated with protocol-imposed interventions will be recorded. After study drug initiation, all AEs and SAEs will be recorded until 4 weeks after either the last administration of study drug or the Early Termination visit. If a subject is discontinued from the study prematurely, AEs and SAEs will be recorded at the Early Termination visit. The Day 208 Safety Follow-up visit is not required if a subject enrolls in the optional, open-label extension study at the Day 183/Month 6 visit. The Month 25 Safety Follow-up visit will be waived if a subject enrolls in the 111-205 extension study at the Month 24/Study Completion visit.
- ^{bb} In the initial phase of the study, on weeks when caregivers/subjects will not see either a home healthcare professional or a study staff member, a phone call by the study staff member to the caregiver/subject will be required. During the call study staff will ask the caregiver about correct administration procedures, assess adverse events (AEs), record concomitant medications, and answer questions. During the optional, open-label extension phase, the call frequency will change to every 2 weeks (\pm 3 days) for the first 6 months of the extension phase and monthly (\pm 5 days) thereafter.

Table 9.1.3: Criteria for Dose Adjustment Visits

Dose Adjustment Recommendation*	Dose Adjustment Made	Dose Adjustment Visit Procedures	Follow-up Phone call	4-week Follow-up Visit (± 2 weeks)	Procedures Done at Follow-up Visit
Next scheduled visit is ≤4 weeks away	At next scheduled visit	The procedures below are done at dose adjustment visits. If the dose adjustment visit happens at a regularly scheduled visit, conduct the remaining scheduled visit procedures as well.	7-10 days post dose adjustment	Schedule 4 weeks after the dose adjustment visit if a regularly scheduled visit does not occur within the visit window	The procedures below are done at adjustment follow-up visits. If the adjustment follow-up visit happens at a regularly scheduled visit, conduct the remaining scheduled visit procedures as well.

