9.3.4 Subject Identification and Replacement of Subjects

Each subject will be assigned a unique subject identifier. This unique identifier will be on all CRF pages.

Subjects who discontinued the study prior to Day 10 may be replaced upon discussion with the DMC. Subjects who discontinued the study after Day 10 of the initial phase will not be replaced.

Duration of Subject Participation

The planned subject participation in this study is 7 months for those subjects who do not continue in the optional, open-label extension phase, and 25 months for subjects who continue. Subjects will receive study treatment daily for 6 months in the initial phase, and 18 months in the optional, open-label extension phase for a total of up to 24 months. Following completion of 6 months, subjects who decline to participate in the extension phase will be followed for safety for an additional 1 month. The safety follow-up assessment will be a telephone call made weekly to the subject's legal guardian to assess for any AEs that may have occurred following completion of dosing. These subjects will return at Day 208 for the Safety Follow-Up visit and exit the study. For subjects who participate in the optional, open-label extension phase, following completion of Month 24, subjects will be followed for safety for an additional month to Month 25. Subjects who participate in the open-label extension phase of study 111-202 will have the option to enroll in the long-term extension study 111-205 at the Month 24/Study Completion Visit. The Month 25 Safety Follow up visit will be waived if a subject enrolls in the 111-205 extension study at the Month 24/Study Completion Visit.

Follow-up assessments and procedures should be performed as outlined in the 111-202 Schedule of Events ([Table 9.1.1](#)).

Subjects who discontinue from study treatment prior to Month 6 will be asked to complete study assessments and procedures for the remainder of the initial phase of the study. Subjects who discontinue from study treatment prior to Month 24 will be asked to complete study assessments and procedures for the remainder of the optional, open-label phase of the study. If subjects discontinue from study treatment and decline to participate for the remainder of the study, they will be asked to return for a final follow-up visit 4 weeks after their last study visit.

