12 EFFICACY EVALUATIONS

Efficacy analysis will be carried out for the initial 6-month period and the entire study period. Figures are reported on the efficacy populations. Summary tables and figures include assessments at 12 months and 6 months prior to screening (-12M and -6M Visits in Study 111-901). [REDACTED]

Some growth parameters were only optional to collect. These parameters are not included in the figures due to the sparse data. They are indicated in the tables [REDACTED]

The mean (or the non-missing measurement in case one of the two measurements is missing) of the two measurements recorded on the anthropometric measurements in the eCRF at each scheduled visit based on analysis windows will be used for the outputs/figures [REDACTED]

All assessments collected during the study are included in the outputs even if they occur following treatment discontinuation

The baseline annualized growth velocity (AGV) is established in the natural history study of Study 111-901, based on the standing height measurements in the 6 months prior to the screening visit of Study 111-202. For all other efficacy endpoints, the Baseline is defined as the last non-missing assessment prior to the first dose of study drug. Unless otherwise specified, efficacy analyses will be performed using available data at derived visits.

In the initial 6-month period, efficacy data will be summarized (absolute measures and change from baseline) by cohort and overall. With the exception of AGV, summaries include measurements from all scheduled assessments. Separate tables with testing are provided just for Day 183 including baseline just for those with assessment at Day 183.

In the entire study period, efficacy data will be summarized for Cohort 3 and Cohort 4 by cohort and Cohort 3 and 4 combined. Summaries include assessments from 12 months prior to screening (-12M Visit in Study 111-901) to up to the Month 24 Visit in study 111-202.

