14 SAFETY EVALUATIONS

Safety analysis will be carried out for the initial 6-month period, the extension period, and the entire study period, respectively. For each of the periods, all subjects who receive at least one dose of study treatment in the corresponding period and have any post-treatment safety information will be included in the safety analysis. Safety will be assessed by examining the incidence, severity grade, and relationship to study drug of all treatment-emergent adverse events (TEAEs) reported during the study period. In addition, all other safety measures including clinical laboratory results, vital signs, electrocardiogram (ECG) and Echocardiogram (ECHO) values will be assessed. Unless otherwise specified, the baseline for safety endpoints is defined as the last non-missing assessment prior to the first dose. Numeric parameters will be summarized by descriptive statistics including n, mean, SD, median, minimum, and maximum. Adverse events will be summarized by number and percentage. Change from baseline will be calculated when both baseline and post-baseline results are non-missing numeric values.

For the initial 6-month period, unless otherwise specified, safety data will be presented for each cohort and all cohorts combined.

For the extension period, unless otherwise specified, safety data are summarized by dose level and all cohorts combined.

For the entire study period, unless otherwise specified, safety data are summarized by dose level and by cohort and all cohorts combined.

Subjects in Cohorts 1 and 2 may be represented at multiple dose levels and accounted once for each dose level they receive. Note the following rules are applied to associate the safety measure to a specific dose:

- AEs are associated to the dose taken on the start date of the AE.
- For mean summaries of safety parameters at visits over the course of the study the assessments on the day of escalation will be summarized under the previous dose.
- For mean summaries assessing pre and post dose measure on a specific day the assessments on the day of escalation will be summarized under the new dose.

For all summary tables for patients who discontinue treatment, all safety assessments within 30 days from the treatment discontinuation date will be included in summary tables.

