14.1 Adverse Events

Adverse events will be coded in accordance with MedDRA version 19.1. A TEAE is defined as any AE that newly appeared or worsened in severity following initiation of study drug administration during the AE reporting period. After informed consent is obtained and the first administration of study drug, all non-serious AEs and SAEs reporting period begins and continues until 4 weeks following either the last administration of study drug or the early termination visit, whichever is longer. If the onset date or end date of an adverse event is partial, the same imputation rules described in Section 9 will be applied.

AEs are summarized by incidence rates and for specific tables also by exposure adjusted incidence rates:

- Incidence rates calculated as number of subjects with the event divided by the number of subjects in the population being assessed
- Exposure-adjusted incidence rates (EAIR) are calculated by dividing the total number of events by the total treatment exposure in the period under assessment for the subjects in the population being assessed. The exposure time for each subject is derived as the time from the date of first dose, to the date of the last dose in the period under assessment.

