14.2 Clinical Laboratory Tests

Summaries are provided for the 6 month period by cohort, the extension period by dose, and the entire study period by dose and by cohort. Descriptive statistics for clinical laboratory tests and change from baseline at each scheduled visit based on analysis windows will be presented.

Shift table from baseline to most extreme post-baseline value (including scheduled and unscheduled visits) based on the CTC grading (Grade 0 - 4 where available) will also be generated for each parameter as appropriate. Percentages are based on the number of subjects with each Baseline CTCAE grade.

All non-missing numeric results will be used to determine CTC grade based on CTCAE v4.0. Summary tables consider all lab assessments from baseline up to 30 days post treatment discontinuation. [REDACTED]

[REDACTED]

Lab parameters assessed

Hematology: (counts for differentials)

Blood Chemistry

Urine: Chemistry

Urinalysis

Other labs

For the initial 6-month period, clinical laboratory tests will be presented for each cohort and all cohorts combined. For the extension period, clinical laboratory tests are summarized by dose level. For the entire study period, clinical laboratory tests are summarized by dose level, by cohort, and all cohorts combined.

Figures are provided for each of the lab parameters summarized in the tables (1) by cohort for the first 6 months (2) by dose for the extension (3) for the entire study period by cohort.

[REDACTED]

- [REDACTED]
- [REDACTED]
- [REDACTED]
- [REDACTED]
- [REDACTED]
- [REDACTED]

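### For children who stop BMN 111 but stay in the study, AE reporting closes 4 weeks after the last dose, so a new AE found later may go unreported and enters no AE summary table

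*Protocol*

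**What the plan says.** **Follow-up after stopping.** Protocol 9.3.4: "Subjects who discontinue from study treatment prior to Month 24 will be asked to complete study assessments and procedures for the remainder" of the open-label phase. The same section has a matching rule for stops before Month 6. Section 9.3.3 waives PK and post-dose measurements for these children and keeps the other assessments where possible. Tables 9.1.1 and 9.1.2 list adverse events at every visit.

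**Reporting period.** Protocol 10.2.1: AE and SAE reporting "continues until 4 weeks following either the last administration of study drug or the early termination visit, whichever is longer". Section 10.4.1 repeats this for expedited SAE reports. Schedule footnote aa gives it without the final clause: "all AEs and SAEs will be recorded until 4 weeks after either the last administration of study drug or the Early Termination visit".

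**Instructions that carry no such limit.** Section 10.2.2 tells investigators to ask about AEs at each patient contact and to record all of them. Section 9.10.4.1 has AEs assessed continuously from consent. Section 10.3.1.6 requires new clinically significant examination findings during the study that meet the AE definition to be recorded.

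**Analysis.** SAP 14.1: "A TEAE is defined as any AE that newly appeared or worsened in severity following initiation of study drug administration during the AE reporting period". SAP 14, for those who discontinue treatment: "all safety assessments within 30 days from the treatment discontinuation date will be included in summary tables". SAP 14.2: "Summary tables consider all lab assessments from baseline up to 30 days post treatment discontinuation". For efficacy, SAP 12 says: "All assessments collected during the study are included in the outputs even if they occur following treatment discontinuation".

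**The concern.** Safety and tolerability are the primary objectives of both phases. The stopping criteria in Section 9.1.1.1 include hip findings, tibial bowing, worsening disproportion and loss of elbow motion, and one listed outcome is permanent discontinuation with continued assessment. The plan therefore expects some children to be followed off drug, possibly for a long time.

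Section 7.1 gives a reason to watch them: "Adverse skeletal changes associated with exaggerated growth were seen in all normal nonclinical species with open growth plates", described there as depending on dose, exposure and time. Hip checks are 6 months apart (Section 9.10.4.4.3), so a change acquired on drug could first be seen well after the last dose. If that finding is a new AE, the reporting period has closed and it is not a TEAE. Cohorts have 8 to 10 children, so one child with an unreported event is 1/10 to 1/8 of a cohort, or 10% to 12.5%.

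**Working it through.** The plan states no figure for this, so the check is a reading of the rules followed by day arithmetic.

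**Step 1: does the early termination limb extend the period?** Under Section 9.3.3 and footnote aa, that visit belongs to a child who leaves the study early. A child who attends through Day 183 or Month 24 has the scheduled final visit instead. Only the last-dose limb applies, and the period ends on stop day + 28. Where a late early termination visit does occur, the period extends but the SAP's 30-day limit does not. An event can then be reportable and a TEAE, yet lie outside the safety tables.

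**Step 2: is there another route for a late event?** Section 10.6 covers SAEs believed related, and only those after the last scheduled visit or after participation has ended. Section 10.7 runs to the last study visit but concerns events that may need urgent safety measures. A new non-serious AE in a child still attending has only the general instructions in 10.2.2, 9.10.4.1 and 10.3.1.6, which conflict with the closed period.

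**Step 3: how much follow-up lies outside?** Inputs are the target days in SAP Table 3.4.2: Day 85, 127, 183, Month 8 = 243, Month 10 = 303, Month 12 = 364, Month 15 = 456, Month 18 = 547, Month 21 = 638, Month 24 = 730. Off-drug days = end day − stop day. Days outside = off-drug days − 28.

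| Stop day | Followed to | Off-drug days | Outside 28 days | Outside 30 days | Next visit, days after stop |
|---|---|---|---|---|---|
| 43 | 183 | 140 | 112 (80%) | 110 (79%) | 85 − 43 = 42 |
| 184 | 730 | 546 | 518 (95%) | 516 (95%) | 243 − 184 = 59 |
| 243 (Month 8) | 730 | 487 | 459 (94%) | 457 (94%) | 303 − 243 = 60 |
| 364 (Month 12) | 730 | 366 | 338 (92%) | 336 (92%) | 456 − 364 = 92 |
| 547 (Month 18) | 730 | 183 | 155 (85%) | 153 (84%) | 638 − 547 = 91 |

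In every row the next visit is beyond day 30, even at the early edge of its protocol window (± 7 days to Month 12, ± 14 days after). A child who stops at Month 8 has 6 of 6 remaining visits outside (Months 10, 12, 15, 18, 21 and 24). A child who stops on Day 43 has 3 of 3 (Days 85, 127 and 183). The safety follow-up visits at Day 208 and Month 25 are not counted.

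**Step 4: stops between visits.** Extension visit targets are at least 60 days apart (303 − 243), so at most one can fall within 30 days of stopping. In the first month of dosing visits are closer together, and several can fall inside. If stop times are uniform over a hip-check interval of 183 days, the next check falls within 30 days with probability 30/183 = 16% (28 days: 28/183 = 15%). Uniform timing is an assumption.

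**The case against.** The case on the other side has substance.

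- **A reader might infer that late skeletal harm drops out of the analysis.** The documents do not support that. Growth measures and body proportions are SAP 12 outputs that keep off-drug data. Imaging (SAP 13.3) and elbow motion (SAP 13.4) use the efficacy population. The plan does not say whether the off-drug rule of SAP 12 or the 30-day rule of SAP 14 governs them. Hip assessments are listed by subject with no time limit (SAP 14.5) and are tabulated for nobody, on or off drug.
- **A reader might infer that a child taken off drug for a hip or bowing finding is the one missed.** That finding arises on drug, inside the period. If recorded as an AE it is a TEAE, and Section 10.5 has unresolved events followed until resolved or stable. Abnormal hip results go to the DMC with no stated time limit (Section 9.10.4.4.3). The gap concerns new events.
- **Late AEs may still be recorded.** Sites are told to ask at each contact, and Protocol 13.4 has all AEs listed. This stands: the documents contradict each other and do not show that late events go unrecorded. A recorded late event would still not be a TEAE.
- **A reader might infer harm that begins after stopping, or a bias towards looking safe.** Section 7.1 does not say that the changes begin or progress after stopping, and the half-life is about 45 minutes. The number of affected children is not given.
- **An on-treatment cut is coherent.** Exposure-adjusted rates in SAP 14.1 use time from first to last dose, so adding late events would distort them. This supports a separate table.
- **Blacked-out text** follows the 30-day laboratory rule in SAP 14.2, so later laboratory data may be dealt with there.

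**Conclusion.** The point holds for AE reporting and the AE summary tables in children who stop drug and stay in the study. For them the period closes 4 weeks after the last dose, with no stated exception, while visits and AE questioning continue. A new AE first found later may go unreported and has no summary table to enter. Across the stop days tabulated, 80% to 95% of off-drug follow-up lies outside the 28-day window.

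This rests on three readings: a child who completes off drug has no early termination visit, the SAP 14 sentence on 30 days is a limit (it says what is included, not what is excluded), and visits fall near their target days. The stop days are illustrations. How many children stop and stay is not stated, so the size and direction of any effect on the safety conclusions are unknown.

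**What to change.** **Protocol.** Reconcile 10.2.1, 10.4.1 and Schedule footnote aa with 10.2.2, 9.10.4.1 and the schedule, so that AEs and SAEs in children followed off drug are recorded to their last study visit, or to 4 weeks after the last dose if that is later. This concerns recording only and changes no dose or stopping rule.

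**SAP 14 and 14.1.** Keep the 30-day on-treatment tables and the exposure-adjusted rates. Add one separate table of AEs with onset more than 30 days after the last dose, by last dose level.

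**SAP 13.** State that the off-drug rule of SAP 12 also applies to the imaging and elbow outputs.

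**Cost.** Wording in both documents and one table. The visits are already scheduled. The downside is a few more AE records that are unlikely to be drug-related, reported separately so that they do not dilute the on-treatment tables.
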